## Study Design:

- Interventional, randomized controlled trial (RCT)
- Two-arm parallel design (Intervention vs. Control)
- Single-blinded (evaluator)

## Study Population:

- Total of 39 terminal-stage cancer patients receiving palliative care
- Intervention group (n = 22), Control group (n = 17)

## Study Protocol and Statistical Analysis Plan on Palliative Study

### **Inclusion Criteria:**

- Age >18 years
- Terminal stage cancer diagnosis
- Receiving inpatient palliative care
- Able to provide consent or have a legal representative

### **Exclusion Criteria:**

- Cognitive impairment preventing exercise compliance
- Severe respiratory instability

### **Intervention Description:**

-The intervention group received structured breathing exercises consisting of pursed-lip breathing, diaphragmatic breathing, respiratory control, relaxation breathing exercises, and slow, deep breathing, once a day for 5 days, for an average of 15 minutes. Exercises administered by a physiotherapist. Conducted once daily for 5 consecutive days

### **Control Group:**

- Receives standard palliative care and an informational booklet that describing breathing exercises.

### **Primary Outcomes:**

1. Pain level (measured by Visual Analog Scale - VAS)
2. Dyspnea (measured by Cancer Dyspnea Scale - CDS)
3. Functionality (measured by ESAS-r functional subscale)

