# Study Protocol and Statistical Analysis Plan on Palliative Study

## **Data Collection Time Points:**

- Baseline (Day 0)
- Post-intervention (Day 5)

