## **Data Analysis:**

- Data analyzed using SPSS Statistics v27
- Kolmogorov-Smirnov test for normality
- t-tests, Wilcoxon signed-rank test, and Mann-Whitney U test as appropriate
- Effect size reported using Cohen's d

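### Three primary outcomes have no stated alpha, success rule or multiplicity control, and no between-arm, baseline-adjusted comparison is assigned to them

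*Combined protocol and SAP*

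**What the plan says.** The Primary Outcomes section numbers three measures: "Pain level (measured by Visual Analog Scale - VAS"), "Dyspnea (measured by Cancer Dyspnea Scale - CDS") and "Functionality (measured by ESAS-r functional subscale"). It does not say whether the numbers are a ranking or a testing order, or whether one, each or all of the outcomes must succeed.

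The Data Analysis section is the only analysis text available. Apart from the software and Cohen's d, it gives "Kolmogorov-Smirnov test for normality" and "t-tests, Wilcoxon signed-rank test, and Mann-Whitney U test as appropriate". It states no significance level or sidedness, and ties no test to a primary outcome.

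Data Collection Time Points gives "Baseline (Day 0") and "Post-intervention (Day 5"). The analysis text does not say whether the Day 5 score, the change from Day 0, or a Day 5 difference adjusted for Day 0 is to be tested. Study Population gives "Intervention group (n = 22), Control group (n = 17").

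**The concern.** Two things are left open, and both bear on the main conclusion.

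- **The success rule.** Claiming benefit on any one outcome, making a separate claim for each, or requiring all three would all be consistent with the text. These rules have very different error rates.
- **The comparison.** The signed-rank test is paired, so in a two-arm trial it normally compares Day 5 with Day 0 within one arm. The t-tests could be paired or two-sample. Nothing limits the within-arm tests to description. Controls receive standard care and a breathing-exercise booklet, so both arms could improve. A significant within-arm change would then say nothing about the difference between arms.

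The plan also collects a Day 0 value for each outcome but names no analysis that adjusts for it. With 39 patients, that may give up precision the trial needs.

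**Working it through.** The plan gives no alpha, power or sample-size figure, so there is none to reproduce.

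**Inputs from the plan:** three primary outcomes; 22 and 17 patients; Day 0 and Day 5 measurements.

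**Assumptions, none stated in the plan:** two-sided 0.05 per test; no true arm difference (steps 1 to 3); equal correlation ρ between outcomes; correlation r between Day 0 and Day 5 (step 5).

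**1. Any one outcome counts.** At ρ = 0: 1 − (1 − 0.05)³ = 1 − 0.857375 = 0.1426. For ρ > 0, let A(u) = Φ((1.96 − √ρ·u)/√(1 − ρ)) − Φ((−1.96 − √ρ·u)/√(1 − ρ)). The risk is 1 − ∫φ(u)A(u)³du.

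**2. All three required.** The risk is 0.05³ = 0.0001 at ρ = 0, and ∫φ(u)(1 − A(u))³du otherwise. With separate claims it is 5% for each claim, whatever ρ is.

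**3. Holm, all three nulls true.** The formula is that of step 1 with the critical value for 0.05/3 = 0.0167.

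| ρ | Any one | All three | Holm |
|---|---|---|---|
| 0 | 14.3% | 0.01% | 4.9% |
| 0.3 | 13.6% | 0.09% | 4.8% |
| 0.5 | 12.5% | 0.3% | 4.5% |
| 0.7 | 10.9% | 0.9% | 3.9% |

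Simulated two-sample t-tests with 22 and 17 patients (200,000 trials per correlation) gave any-one rates of 14.2%, 13.8%, 12.5% and 10.9%.

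**4. Hypothetical: within-arm tests read as benefit.** Suppose both arms improve equally by m SDs of change, so there is no difference between arms. In the intervention arm each paired t statistic is noncentral t with 21 df and noncentrality m√22 (for m = 0.3, 0.3 × 4.69 = 1.41). Simulating three outcomes at ρ = 0.5 (100,000 trials), at least one significant improvement appears in about 30% of trials at m = 0.2, 49% at 0.3 and 85% at 0.5. The values of m are assumed.

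**5. Power cost of Holm's first step.** The factor for 22 and 17 is √(22 × 17/39) = 3.097. An effect of 0.929 SD gives noncentrality 0.929 × 3.097 = 2.88 on 37 df. Power is 80% at 0.05 and 64% at 0.0167. The value 0.929 is simply the effect with 80% power at 0.05; the plan names no target.

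Adjusting for Day 0 multiplies the residual SD by √(1 − r²), which is √0.75 = 0.866 at r = 0.5, and uses one more degree of freedom. At r = 0.5, power is about 89% at 0.05 and 77% at 0.0167. First-step power with adjustment is 63%, 68%, 77% and 92% at r = 0, 0.3, 0.5 and 0.7, against 64% without adjustment.

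**The case against.** The strongest reply is that the plan never says one significant result out of three is success. Pain, dyspnea and functionality are distinct constructs, so separate claims at 5% each are a natural reading, and on that reading nothing is inflated. This stands. A reader might infer that the plan has an 11-14% error rate, but the documents support only that the rule is unstated and that 11-14% is the result under one of the possible rules.

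A reader might also infer that the open test menu pushes the error much higher. Taking the smallest p-value from t-test or Mann-Whitney, on Day 5 score or change, would give 22-30% for any one outcome and 8-11% even with Holm. That is a bound needing deliberate selection, and the documents show none. The listed normality check suggests that its result picks the test. Simulating that choice on Day 5 scores gave 5.0-5.2% per outcome, 11.2-14.6% for any one and 4.1-4.9% with Holm, so the check itself adds almost nothing.

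Nor does a signed-rank test in the menu make it the primary comparison. The Study Design section describes a parallel comparison of two arms, and Mann-Whitney is a between-arm test. The 30-85% figures are therefore hypothetical. What remains is that no between-arm test is assigned to any primary outcome.

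Finally, other rules would also close the multiplicity gap, such as a single primary outcome, a fixed order or all three required. That is true. Holm is suggested because it needs no ranking, and the plan states none.

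**Conclusion.** The concern holds in conditional form and should be fixed. The available text fixes neither the alpha, nor the success rule, nor the between-arm comparison for the three primary outcomes, and it makes no use of Day 0 as a covariate. Some front matter was not available, so the absence is asserted only for the text that was.

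At an assumed two-sided 0.05, the risk of a false primary claim is about 11-14% under an any-one rule (ρ from 0.7 to 0), 5% per claim under separate claims, and at most 0.9% for ρ up to 0.7 if all three are required. Reading within-arm change as benefit would be a further, separate route to a false claim.

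It would go too far to say that results were selected, or that baseline adjustment pays for Holm. Adjustment is a separate gain that grows with the Day 0-Day 5 correlation. At zero correlation there is no gain and a slight loss (63% against 64% at the first step).

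**What to change.** In the Data Analysis section:

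1. For each primary outcome, name one primary comparison: the Day 5 difference between arms adjusted for the Day 0 value, from a linear model of Day 5 score on arm and Day 0 score with a two-sided test of the arm term.
2. Make Mann-Whitney a sensitivity analysis and within-arm paired tests descriptive only.
3. State a familywise two-sided alpha of 0.05 and apply Holm to the three p-values: smallest against 0.0167, next against 0.025, largest against 0.05, stopping at the first failure.
4. Report all three arm differences with 95% confidence intervals, whatever the outcome of testing.

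Study Timeline gives completion as May 2025. If the data have already been analysed, label both the comparison and the Holm procedure as post hoc. That limits over-claiming but does not restore prespecification.

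The change affects analysis and reporting only and uses data already planned. Its price is power at Holm's first step. With 22 and 17 analysed and a true effect of 0.93 SD, the like-for-like loss is 80% to 64% without baseline adjustment, or about 89% to 77% with it at a Day 0-Day 5 correlation of 0.5.

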### **Secondary Outcomes:**

- SpO2, pulse rate, hemoglobin, leukocyte, platelet, CRP levels

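### The plan names no log scale and no baseline adjustment for the skewed laboratory outcomes; for CRP compared as raw change this costs substantial power, and for leukocytes and platelets a moderate amount.

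*Combined protocol and SAP*

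**What the plan says.** The Secondary Outcomes section lists "SpO2, pulse rate, hemoglobin, leukocyte, platelet, CRP levels" without units, scale or summary measure. Data Collection Time Points gives two measurements, "Baseline (Day 0" and "Post-intervention (Day 5" being the labels. Study Population gives 22 intervention and 17 control patients.

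The Data Analysis section is the whole statistical plan. It names the software, a "Kolmogorov-Smirnov test for normality", then "t-tests, Wilcoxon signed-rank test, and Mann-Whitney U test as appropriate", and finally "Effect size reported using Cohen's d". It does not mention a log transformation, a ratio measure or a model with the Day 0 value as covariate. It does not say which quantity (Day 5 value or change from Day 0) is compared between arms. It gives no significance level, SD, correlation or expected effect for any outcome.

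**The concern.** CRP, leukocyte and platelet values are positive concentrations or counts. Their spread usually grows with their level, and an effect on them is naturally read as a percentage. If such values are analysed in original units as changes, a small percentage change in a patient with high CRP counts for more than a large percentage change in a patient with low CRP. A rank test on raw changes does not remove this, because the order of absolute changes is not the order of ratios.

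If only Day 5 values are compared, each patient's own starting level is thrown away although it was measured.

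At stake is the ability of 39 patients to show a real proportional effect on these markers, and whether the reported effect size describes a typical patient. Cohen's d is a mean difference divided by an SD, and in raw CRP both can be driven by a few high values.

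**Working it through.** The plan states no power, effect or SD for these outcomes, so there is no figure to reproduce. The check compares the analyses that the plan leaves open with a log-scale analysis of the same data.

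**Inputs from the document:** 22 and 17 patients; Day 0 and Day 5; t-test or Mann-Whitney between arms. (The Wilcoxon signed-rank test is a paired test within an arm and gives no between-arm comparison.)

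**Assumed, because the document is silent:** two-sided 5%; log-normal values; a constant proportional effect. CRP-like: log-SD 1.0, Day 0 to Day 5 log correlation 0.7, true ratio 0.6. Count-like: log-SD 0.4, correlation 0.7, ratio 0.8.

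**Step 1. Log scale, by formula.** With standardised effect d, the noncentrality is d × √(22 × 17 / 39) = d × 3.097. For CRP, |ln 0.6| = 0.511.

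- Log Day 5 alone: SD = 1.0; d = 0.511; noncentrality 1.58; power about 34%.
- Log change: SD = 1.0 × √(2 × (1 − 0.7)) = 0.775; d = 0.511 / 0.775 = 0.66; noncentrality 2.04; power about 51%.
- ANCOVA on log Day 5 with log Day 0 as covariate: residual SD = 1.0 × √(1 − 0.7²) = 0.714; d = 0.511 / 0.714 = 0.716; noncentrality 2.22; power about 58% (slightly less once the covariate is estimated).

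For counts, |ln 0.8| = 0.223. Log change has SD 0.4 × 0.775 = 0.310, d = 0.72, noncentrality 2.23 and power about 58%.

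**Step 2. All analyses, by simulation, CRP-like case.**

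| Analysis | Power |
|---|---|
| Raw change, t-test | about 24% |
| Raw change, Mann-Whitney | about 35% |
| Raw Day 5, t-test | about 18% |
| Raw Day 5, Mann-Whitney | about 32% |
| Log Day 5, t-test | about 32–34% |
| Log change, Mann-Whitney | about 49% |
| Log change, t-test | about 52% |
| Log ANCOVA | about 57% |

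The simulated log-scale results agree with Step 1.

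**Step 3. Separate scale from baseline.**

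- Scale, same test on change: t-test 24% to 52%; Mann-Whitney 35% to 49%.
- Scale, Day 5 values: Mann-Whitney depends only on ranks, so its p-value is identical on raw and log values. It reaches about 32%, against about 32–34% for the log t-test, so almost nothing is lost to scale.
- Baseline, on the log scale: Day 5 alone about 32–34%, ANCOVA about 57%. This accounts for the gap between Mann-Whitney on Day 5 and the better analysis.

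**Step 4. Vary the assumptions (CRP, ratio 0.6).** The columns give power for raw change by t-test, raw change by Mann-Whitney, Day 5 by Mann-Whitney, and log change by t-test.

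| Log-SD, correlation | Raw change t | Raw change MW | Day 5 MW | Log change t |
|---|---|---|---|---|
| 0.8, 0.7 | 40% | 51% | 47% | 70% |
| 1.2, 0.7 | 15% | 26% | 24% | 38% |
| 1.0, 0.5 | 17% | 24% | 33% | 34% |

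In the last row log change gains almost nothing over Mann-Whitney on Day 5 values; log ANCOVA still reaches about 42%.

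**Step 5. Let the normality check choose the test.** With log-SD 1.0, correlation 0.8 and ratio 0.56, the Kolmogorov-Smirnov-guided choice on raw change has 56% power (with Lilliefors correction) or 48% (without), against 79% for a t-test on log change. The effect is missed in 44–52% of trials instead of 21%.

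**Step 6. Counts.** At log-SD 0.4 and ratio 0.8, raw change has about 48% by either test against 58% on log change, a loss of 10 points.

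**Step 7. False positives.** With no true effect, every method rejects in about 3–5% of trials.

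**Step 8. Summary measure.** In the CRP-like case, three of the 39 patients typically supply about 67% of the sum of squares of the raw changes. That sum is what the SD in Cohen's d is built from.

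**The case against.** The strongest reply is that the plan already provides rank tests for non-normal data, and these limit the pull of extreme values. For Day 5 values this stands in full: Mann-Whitney is unaffected by taking logs, and with the Lilliefors correction the normality check would send CRP-like Day 5 values to it in 95–99% of simulated trials (35–53% without the correction). For raw changes it does not stand, as Steps 3 and 5 show.

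A reader might infer that the scale problem holds whichever listed test is used, that effects on all three markers would be missed far more often, or that two or three patients would decide the test results. The documents do not support these readings. Mann-Whitney on Day 5 values has no scale problem, only a baseline one; the loss for counts is moderate; and rank tests bound the influence of single patients. Nor do the documents state that raw changes will be analysed. That is one reading of their silence.

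It is also fair to say that the sample size limits power on either scale. At log-SD 1.2 the t-test on log change still misses the effect in 62% of trials. And every spread, correlation and effect here is assumed, including a 40% CRP reduction after five daily sessions.

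**Conclusion.** The point holds mainly for CRP. If CRP is compared as raw change, power under the stated assumptions is about 24% (t-test) or 35% (Mann-Whitney), against about 52% for a t-test on log change and 57% for log ANCOVA. If Day 5 values are compared by Mann-Whitney, the shortfall (about 32% against 57%) is due to the unused baseline. Either between-arm route that the plan leaves open is therefore weaker than a log-scale analysis adjusted for Day 0, for different reasons. For leukocytes and platelets the raw-change loss is about 10 points.

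Cohen's d on raw CRP is a poor summary whichever test is used.

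The size of the gain depends on log-normal values, a proportional effect, and the assumed spread and correlation. It is a loss of efficiency, not of validity. It touches secondary outcomes only; pain, dyspnea and functionality are unaffected.

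**What to change.** Add to the Data Analysis section:

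- CRP and, for consistency, leukocyte and platelet counts are natural-log transformed before analysis.
- The arms are compared by ANCOVA on log Day 5 with log Day 0 as covariate.
- The result is reported as a ratio of geometric means with 95% CI, in place of Cohen's d on raw values.
- A rule is stated in advance for CRP below the assay limit.

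The Study Timeline gives completion in May 2025. If data collection is already complete, the analysis should be labelled as a later change.

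The cost is wording and reanalysis of values already scheduled at Day 0 and Day 5; no new patients, visits or measurements are needed. The drawback is that results read as ratios rather than in laboratory units. Raw medians by arm and day can be shown alongside.

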# Study Protocol and Statistical Analysis Plan on Palliative Study

## **Data Collection Time Points:**

- Baseline (Day 0)
- Post-intervention (Day 5)

## **Data Analysis:**

- Data analyzed using SPSS Statistics v27
- Kolmogorov-Smirnov test for normality
- t-tests, Wilcoxon signed-rank test, and Mann-Whitney U test as appropriate
- Effect size reported using Cohen's d

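### The plan names no baseline-adjusted comparison of the arms and does not fix whether they are compared on Day 5 values or on change, which costs precision and leaves a choice open

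*Combined protocol and SAP*

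**What the plan says.** The Data Analysis section is the whole statistical plan. It names the software, a Kolmogorov-Smirnov check of normality, "t-tests, Wilcoxon signed-rank test, and Mann-Whitney U test as appropriate", and Cohen's d as effect size. The signed-rank test is a within-arm test and the Mann-Whitney U test a between-arm test. The t-tests are not identified as paired or independent. No covariate-adjusted model appears.

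The Data Collection Time Points section gives two visits, "Baseline (Day 0" and "Post-intervention (Day 5" in its notation. There is no table of outcomes by visit, so I take both visits to apply to every outcome. No section says whether the arms are compared on the Day 5 value or on the change from Day 0, and Cohen's d carries the same ambiguity. The Study Design section describes a randomized, two-arm parallel trial, and Primary Outcomes lists three measures: VAS pain, CDS dyspnea and the ESAS-r functional subscale.

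**The concern.** In a randomized parallel trial, the between-arm contrast is the one that randomization supports, and here it is the one left undefined. Two things follow.

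First, a comparison of Day 5 values ignores the baseline, and a comparison of change subtracts all of it. Which is more precise depends on the Day 0 to Day 5 correlation and on the two SDs, none of them known in advance. ANCOVA estimates the weight to give the baseline and so avoids that bet.

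Second, the Day 5 difference minus the change difference equals the Day 0 gap between the arms. With 39 patients that gap is often not small, so the two readings of the plan can give different answers on the same data. If someone chose between them after seeing both, the nominal error rate would no longer hold.

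**Working it through.** The plan gives no alpha, power, effect size or SD, so there is no stated figure to reproduce.

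**Inputs from the documents:** 22 and 17 patients (Study Population); one baseline and one follow-up visit (Data Collection Time Points).

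**Assumptions, not in the documents:** two-sided 0.05; normal data; equal SDs at both visits unless stated; no dropout; correlation r from 0.1 to 0.7; true effect d of 0.5 or 0.8 Day 5 SDs.

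**1. Precision.** The SE of a raw difference is sqrt(1/22 + 1/17) = 0.323 SD. Variances relative to the Day 5 comparison are:
- Day 5: 1
- change: 2(1 - r)
- ANCOVA: (1 - r²)(1 + 1/35), where 1/35 = 1/(39 - 4) is the small-sample cost of estimating the slope

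At r = 0.5, change is 1.00 and ANCOVA is 0.75 × 1.0286 = 0.771, so the gain is 1/0.771 = 1.30.

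| r | SE Day 5 | SE change | SE ANCOVA | Gain in effective patients over better simple test | Over worse simple test |
|---|---|---|---|---|---|
| 0.1 | 0.323 | 0.433 | 0.326 | -2% | +77% |
| 0.3 | 0.323 | 0.382 | 0.312 | +7% | +50% |
| 0.5 | 0.323 | 0.323 | 0.284 | +30% | +30% |
| 0.7 | 0.323 | 0.250 | 0.234 | +14% | +91% |

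There is no gain where (1 - r²)(36/35) ≥ 1, that is r ≤ 1/6 = 0.17, or where (1 + r)(36/35) ≥ 2, that is r ≥ 0.94. With s = SD0/SD5, the change variance is (1 - r²) + (s - r)². Both simple variances are therefore at least 1 - r², and under the linear model the loss cannot exceed 1 - 35/36 = 2.8% for any r or SD ratio.

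**2. Power** (noncentral t, 37 df, or 36 for ANCOVA), as Day 5 / change / ANCOVA:

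| r | d = 0.5 | d = 0.8 |
|---|---|---|
| 0.1 | 33 / 20 / 32% | 67 / 44 / 67% |
| 0.3 | 33 / 25 / 34% | 67 / 53 / 70% |
| 0.5 | 33 / 33 / 40% | 67 / 67 / 78% |
| 0.7 | 33 / 50 / 55% | 67 / 88 / 91% |

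**3. How far the two readings diverge.** A Day 0 gap larger than 0.3 SD has probability 0.353 (0.3/0.323 = 0.93 standard errors, two-sided). At r = 0.5 a gap of 0.3 SD shifts the Day 5 estimate by +0.15 SD and the change estimate by -0.15 SD. In simulation, the two t-tests disagree on p < 0.05 in 26, 30 and 39% of trials at d = 0.5 and 31, 30 and 31% at d = 0.8, for r = 0.3, 0.5 and 0.7. At r = 0.1 the figures are 24% and 33%. Part of this is simply that the two tests differ in power.

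**4. Type I error** (simulated, no true effect). A single t-test or Mann-Whitney U test on a pre-fixed quantity rejects in 4.5-5.4% of trials with normal data. Reporting the smaller p of the Day 5 and change t-tests rejects in 8.5, 8.9, 9.2 and 9.5% at r = 0.1, 0.3, 0.5 and 0.7 (100,000 trials per setting). Picking freely between t-test and Mann-Whitney as well gives about 10-11%.

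**5. Where ANCOVA does worse.** For a lognormal outcome with a true effect of 0.8 SD on the log scale and r = 0.5, power is 65-66% for Mann-Whitney, 51% for ANCOVA on the original scale, 75% for rank-based ANCOVA and 78% for ANCOVA on the log scale.

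**The case against.** The strongest reply is that the listed tests are valid. A short public plan that omits the compared quantity does not thereby inflate anything; inflation needs a choice that depends on the results, and a choice made blind to them keeps 5%. That stands. A reader might infer from the open wording that the trial's type I error is inflated, or that someone picked the better result. The documents support neither.

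A reader might also take 10-11% as the error rate under this plan. That figure requires the choice between t-test and Mann-Whitney to be made on results too. The plan lists a normality check just before those tests, and the ordinary reading is that the check selects the test, although no rule is written. Simulating that reading (Kolmogorov-Smirnov with Lilliefors correction in each arm, t-test if both pass, one fixed quantity, 4,000 null trials) gives 4.7% for normal and 5.2% for lognormal data. On that reading the open point is only Day 5 versus change.

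It is also fair to say that the benefit of ANCOVA is an efficiency argument resting on an assumed r, and that on the original scale it can lose to Mann-Whitney when data are strongly skewed. Both points stand and shape the fix. They do not supply the missing definition of the between-arm comparison.

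**Conclusion.** The omission is certain from the text: no baseline-adjusted between-arm analysis is named, and the compared quantity is not stated. It is worth fixing as a cheap improvement; it does not make the listed tests invalid.

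If the quantity was chosen without sight of the results, the cost is precision. Against the better simple test, ANCOVA's effect runs from a 2% loss to a 30% gain in effective patients for r from 0.1 to 0.7; against the worse one the gain is 30% to 91%. If the quantity was chosen after seeing results, the worst case is about 9% per outcome (8.5-9.5%), before any multiplicity across the three primary outcomes. Nothing in the documents shows that this happened.

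Confidence is high for the omission and lower for the size of the benefit, because r, the SDs and the distributions are all absent from the documents. The bound of about 3% on ANCOVA's loss holds under a normal linear model and not for strongly skewed outcomes.

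**What to change.** - For each of the three primary outcomes, name as the between-arm analysis an ANCOVA of the Day 5 value on arm and the Day 0 value of the same outcome. Report the adjusted mean difference with its 95% CI.
- State that inference rests on this comparison and not on within-arm tests.
- Fix the scale for each outcome without sight of the results. Name a rank-based ANCOVA in advance for outcomes expected to be strongly skewed, or otherwise as a sensitivity analysis.
- Keep the t-test (stated as independent) and the Mann-Whitney U test as sensitivity analyses on one stated quantity, Day 5 or change.

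The cost is SAP wording and one model per outcome in the software already planned; no new data are needed. The downsides are one degree of freedom (37 to 36), a loss of up to about 3% of effective patients if r is near zero, and lower power than Mann-Whitney on the original scale for a strongly skewed outcome (about 51% versus 65% in the lognormal example).

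The document describes the intervention in the past tense ("The intervention group received structured breathing exercises") and gives May 2025 as completion, so the change may come after the data. If outcome data have already been seen, label the ANCOVA as post hoc, report it beside the listed tests, and say which quantity those tests compared.

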## **Study Timeline:**

- Start Date: October 2024
- Completion Date: May 2025

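### Does the plan need a stated analysis population and a rule for patients without a Day-5 score?

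*Combined protocol and SAP*

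**What the plan says.** The combined protocol and SAP describes a randomised trial with "Two-arm parallel design (Intervention vs. Control" arms. Eligible patients are palliative inpatients (Inclusion Criteria: "Terminal stage cancer diagnosis"), and one of the two exclusions is "Severe respiratory instability". The first of three primary outcomes is "Pain level (measured by Visual Analog Scale - VAS"; the other two are dyspnea on the CDS and function on the ESAS-r. Outcomes are recorded at baseline and once more, under "Post-intervention (Day 5".

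Study Population gives "Intervention group (n = 22), Control group (n = 17", 39 in all. It does not say whether these are patients randomised or patients assessed, and no allocation ratio is stated.

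Data Analysis lists the software, a normality test, "t-tests, Wilcoxon signed-rank test, and Mann-Whitney U test as appropriate", and Cohen's d. From Study Design to Study Timeline there is no definition of the analysis population, no rule for a missing Day-5 score, and no imputation or sensitivity analysis.

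**The concern.** Patients this ill may die, become unable to answer, or be discharged within five days. With one post-baseline time point there is no later score to fall back on. The named tests need an observed Day-5 value, or a Day 0 and Day 5 pair, so a patient without one leaves the comparison by default.

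If loss, or the reasons for it, differs between arms and relates to outcome, the arms compared are no longer the arms randomised. Losing the sickest patients from one arm flatters that arm; discharge of the fittest does the reverse. Only the intervention arm has daily physiotherapist sessions to miss, so an unstated exclusion for poor adherence could act on one arm alone. All three primary outcomes would be exposed, and a reader without the counts could not tell.

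**Working it through.** The plan states no alpha, power, target effect, SD or dropout rate, so it has no figure to reproduce. The only numerical inputs from the document are 22 and 17 (Study Population). Everything else below is an assumption: two-sided alpha 0.05, outcome in SD units, higher meaning worse.

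**Scale.** The standard error of the difference is √(1/22 + 1/17) = 0.323 SD. The difference detectable with 80% power is (1.960 + 0.842) × 0.323 = 0.905 SD.

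**Is the split itself a sign of loss?** Under simple 1:1 randomisation of 39 patients, a split at least as uneven as 22 to 17 has probability 0.52. It says nothing about loss.

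**Bias by formula.** Let m be the fraction missing in an arm and g the amount by which the missing would have scored worse than the observed. The bias (intervention minus control) is −(m_int × g_int − m_ctl × g_ctl).

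- 2/22 and 2/17 missing, same g of 0.5 to 1.5: −(0.091 − 0.118) × g = 0.01 to 0.04 SD.
- 1/22 and 4/17 missing, g = 1: −(0.045 − 0.235) = +0.19 SD, against the intervention.
- 5/22 and 0/17 missing, g = 1.5: −0.227 × 1.5 = −0.34 SD, favouring the intervention.
- 20% missing in both arms for opposite reasons (g = +1.0 and −0.5): −(0.20 + 0.10) = −0.30 SD.

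**Type I error by simulation.** No true effect, 40,000 replicates, standard normal Day-5 outcome. A latent severity score has correlation rho with outcome, and the most severe patients are removed so that 22 and 17 remain.

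| Lost (intervention, control) | rho | Absolute bias, SD | t-test type I error |
|---|---|---|---|
| 1, 0 | 0.3; 0.5 | 0.028; 0.045 | 5.0%; 5.3% |
| 0, 1 | 0.3; 0.5 | 0.033; 0.051 | 5.1%; 5.4% |
| 2, 1 | 0.3; 0.5 | 0.014; 0.024 | 5.2%; 5.7% |
| 1, 2 | 0.3; 0.5 | 0.036; 0.053 | 5.4%; 5.6% |
| 3, 0 | 0.3; 0.5 | 0.065; 0.109 | 5.7%; 6.7% |
| 0, 3 | 0.3; 0.5 | 0.077; 0.132 | 5.6%; 7.4% |
| 3, 0 | 1.0 | 0.213 | 12.7% |
| 0, 3 | 1.0 | 0.260 | 14.6% |

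A check on one row: 0.132 / 0.323 = 0.41 standard errors, and Φ(−1.55) + Φ(−2.37) is about 7%, in line with the simulated 7.4%.

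If 22 and 17 are instead the numbers randomised, three lost from one arm gives 0.072 to 0.147 SD and 5.7% to 7.3% at rho 0.3 to 0.5. Three lost in each arm, with loss tied to outcome in one arm only, gives 0.064 to 0.130 SD and 5.8% to 6.9%. Loss of 10% in both arms by the same mechanism gives no bias and 5.1% to 5.5%.

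Two limits apply. Rho links outcome to latent severity; the resulting correlation between outcome and being lost is lower, about 0.12 to 0.31 at rho 0.3 to 0.5. The simulation compares Day-5 scores only and does not carry over to change scores.

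**Would a worst-rank Mann-Whitney analysis help?** With loss unrelated to score and no true effect, it rejects in 8.1% (three intervention patients lost), 10.6% (three controls) and 21.2% (five controls), while the t-test stays near 5%. At an assumed 0.8 SD effect with 10% loss per arm, its power is 46.8%, 47.8% and 58.5% at rho 0.3, 0.5 and 1.0, against 63.4%, 65.2% and 77.8% for the t-test.

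**The case for a change.** The strongest case for a change is that the omission is plain and the population is about as prone to early loss as any. Equal counts would not settle the matter, since loss for different reasons can bias the comparison even when the numbers match. Bias can reach 0.30 to 0.34 SD under harsher assumptions, and type I error can reach 14.6%. A count table and one sentence on the analysis set cost almost nothing and could still be supplied after the stated "Completion Date: May 2025".

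Part of this stands. The document is silent, and a careful report should give the numbers randomised and scored in each arm, with reasons for any loss, and analyse every scored patient in the assigned arm. But that only writes down what an analyst would do and a reader would expect; it alters no test, endpoint or comparison. The larger figures need four or five patients lost almost wholly from one arm, 20% loss in each arm for opposite reasons, or losses that fall exactly on the worst scorers. Nothing in the document points to any of these, while the five-day window, the inpatient setting and the exclusion of unstable breathing make heavy loss less likely.

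**Conclusion.** The gap is real but minor, and it does not call for a change to the plan. The exclusion of unscored patients follows from silence, not from a stated rule, and no loss is documented. If all randomised patients were scored, the effect is zero. With one to three patients lost and moderate dependence on outcome, the bias is about 0.01 to 0.15 SD in either direction. The upper end is about one sixth of the detectable difference (0.147 / 0.905 = 0.16).

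The only substantive change of method on offer, worst-rank scoring, is a trade-off. It can reject because of one-sided loss alone, it loses power, and it turns each outcome into a composite of score and loss. If only deaths and patients unfit to be assessed take the worst rank, it also leaves discharge untouched. It would be optional, and post hoc if data have been seen.

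This conclusion assumes few losses over five days and a Day-5 comparison between arms. Heavy loss, one-sided and closely tied to outcome, would change it; patient numbers by arm in the trial report would show that.
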